9.9.2.2 CR RATE

CR rate is defined as the percent of subjects who achieve a CR. CR rate will be analyzed via chi square test. The 95% confidence intervals for the response rates as well as for the differences of the complete

response rate will be presented. Additional logistic analyses model may be used to assess the impact of demographic and baseline parameters.

9.9.2.3 DURATION OF RESPONSE

Duration of response (DOR) defined as the interval from the first documentation of CR or PR to the

UTX-TGR-203

Dated: 20 December 2018 (Ver 2.0)

earlier of the first documentation of definitive disease progression or death from any cause. This variable will be summarized. Estimates of median DOR will be made using Kaplan-Meier methods.

10 SAFETY REPORTING AND ANALYSIS

10.1 SAFETY ANALYSES

The safety population will include all subjects who received any study medication. The safety endpoints will include:

- Incidence of AEs and AEs considered to be drug-related
- Incidence of Grade 3 and Grade 4 AEs
- Incidence of SAEs
- Laboratory values

The safety endpoints will be listed and/or summarized. No inferential statistical analyses will be performed. All subjects who have received at least one dose of ublituximab and/or umbralisib will be included in the safety population.

The analyses of safety will be based on the frequency of adverse events and their severity for subjects in each portion who received at least one dose of study treatment. Worst toxicity grades per subject will be tabulated for select adverse events and laboratory measurements by using NCI CTCAE criteria v4.0.

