10.3 DEFINITIONS OF ADVERSE EVENTS

An adverse event (AE) is any untoward medical occurrence in a subject or clinical investigation subject administered a pharmaceutical product. An AE does not necessarily have to have a causal relationship with this treatment. An adverse event (AE) can therefore be any unfavorable and unintended sign (including an abnormal laboratory finding, for example), symptom, or disease temporarily associated with the use of a medicinal product, whether or not considered related to the medicinal product. This includes any occurrence that is new in onset or aggravated in severity or frequency from the baseline condition.

In clinical studies, an AE can include an undesirable medical condition occurring at any time, including run-in or washout periods, even if no study treatment has been administered. The NCI Common Terminology Criteria for Adverse Events (CTCAE) v4.0 is to be used for the grading of

severity of symptoms and abnormal findings. For adverse events not covered by the NCI-CTCAE Version 4.0 grading system, the following definitions will be used:

- **Grade 1:** Mild; asymptomatic or mild symptoms; clinical or diagnostic observations only; intervention not indicated.
- **Grade 2:** Moderate; minimal, local or non-invasive intervention indicated.
- **Grade 3:** Severe or medically significant but not immediately life-threatening; hospitalization or prolongation of hospitalization indicated.
- **Grade 4:** Life-threatening consequences; urgent intervention indicated.
- **Grade 5:** Death related to AE.

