10.4 ADVERSE EVENTS (AE'S) AND TREATMENT EMERGENT ADVERSE EVENTS (TEAE'S)

All AEs and SAEs occurring on study will be listed by subject. The frequency and percentages of subjects with treatment-emergent adverse events (TEAEs) will be tabulated by system organ class (SOC) and preferred term (PT), where treatment-emergent is defined as any AE that:

- Occurs after first dosing of study medication and through the end of the study or up through 30 days after the last dose of study treatment, or
- Is considered treatment-related regardless of the start date of the event, or
- Is present before first dosing of study medication but worsens in intensity or the investigator subsequently considers treatment-related.

TEAEs that are considered at least possibly related to study treatment will be tabulated as well as deaths, SAEs, and events resulting in treatment discontinuation.

AEs that occur after informed consent but before first dosing of study medication will not be summarized but will be listed.

At each level of summarization, a subject will be counted only once for each AE, SOC, or PT experienced within that level. In the summation for AE severity, within each level of AE, SOC, or PT experienced, the one with the highest severity will be included. In the summation for AE's relationship to the study drug, within each level of AE, SOC, or PT experienced, the one with the closest relationship to the study drug will be included.

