10.9.1 PERSISTENT OR RECURRENT ADVERSE EVENTS

A persistent AE is one that extends continuously, without resolution, between subject evaluation time points. Such events should only be recorded once on the SAE Report Form and/or the AE eCRF. If a persistent AE becomes more severe (changes from a Grade 1 or 2 AE to a Grade 3 or 4 AE) or lessens in severity (changes from a Grade 3 or 4 AE to a Grade 1 or 2 AE), it should be recorded on a separate SAE Report Form and/or AE eCRF.

A recurrent AE is one that occurs and resolves between subject evaluation time points, and subsequently recurs. All recurrent AEs should be recorded on an SAE Report Form and/or AE eCRF for each recurrence.

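### The severity endpoint stops at Grade 4, so the listed severe-AE incidence can fall when an event becomes fatal

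*Combined protocol and SAP*

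**What the plan says.** Section 10.1 lists the safety endpoints. The one that measures severity is "Incidence of Grade 3 and Grade 4 AEs"; the same list has the incidence of all AEs, of drug-related AEs and of SAEs. The section adds that "Worst toxicity grades per subject will be tabulated for select adverse events and laboratory measurements", without naming the events selected, and rules out inferential analysis of safety.

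Section 10.3 grades severity by CTCAE v4.0 and prints a five-level scale for events that CTCAE does not cover. Grade 5 on that scale is "Death related to AE".

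Section 10.4 sets the counting rules for treatment-emergent AEs: "a subject will be counted only once for each AE, SOC, or PT experienced within that level", and for severity, "within each level of AE, SOC, or PT experienced, the one with the highest severity will be included". Treatment-related events "will be tabulated as well as deaths, SAEs, and events resulting in treatment discontinuation".

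Section 10.9.1 has a persistent AE recorded once, with a separate record when it "changes from a Grade 1 or 2 AE to a Grade 3 or 4 AE" or moves back down. A move to Grade 5 is not listed.

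Section 10.9.3 places deaths that the investigator attributes solely to progression on the Adverse Event page of the eCRF, exempt from expedited reporting.

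**The concern.** A measure of severe toxicity should not improve when an event gets worse. If a subject is shown at the highest grade reached, and the severity endpoint covers Grades 3 and 4 only, a Grade 3 pneumonia counts while the subject survives it and stops counting, for that term and system organ class, once it is fatal.

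Safety is a key secondary objective (Section 2.1), and this is the only listed endpoint that summarises AEs by severity. The protocol's own usage is mixed. Section 1.2.2.1 reports earlier single-agent umbralisib safety at Grade 3 or higher, and the run-in toxicity definition in Section 4.2 uses that threshold, whereas Section 1.3.2 describes ublituximab at Grade 3/4. A Grade 3 and 4 figure from this trial would not be on the same basis as the umbralisib figure that the protocol cites.

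**Working it through.** The protocol states no AE rate or expected number of fatal AEs, so there is no figure to reproduce. The check is to read the rules together and then scale the result.

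**Step 1: which grades the endpoint covers.** Section 10.1 names Grades 3 and 4. Nothing in the safety analysis sections adds Grade 5 or defines a summary of Grade 3 and above.

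**Step 2: where a fatal AE falls under each way of counting.**

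- *Highest grade (Section 10.4).* The event sits at Grade 5 for its preferred term and system organ class, outside Grades 3 and 4. If the rule is also applied to an overall any-AE figure, the subject leaves that figure too, even with other Grade 3 or 4 events. Section 10.4 frames the rule by AE, class or term and does not clearly cover the overall figure.
- *Any recorded Grade 3 or 4 event.* Section 10.1 does not itself tie the endpoint to worst grade, so this reading is open. The subject stays in if a Grade 3 or 4 record exists. Under Section 10.9.1, an event that rose from Grade 1 or 2 to Grade 3 or 4 before death leaves one. An event that began at Grade 3 and became fatal need not. For the overall figure, another Grade 3 or 4 event also keeps the subject in.
- *Fatal at onset.* The event has no Grade 3 or 4 record, so it is outside the endpoint for its term under either rule.

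**Step 3: size.** Inputs: N = 50, the planned maximum (Section 4.1), taken as all treated; f = number of subjects whose fatal AE removes them from the Grade 3 and 4 count (assumed).

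Shortfall = 100 × f / N percentage points.

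- f = 1: 100 × 1/50 = 2.0 points
- f = 2: 100 × 2/50 = 4.0 points
- f = 3: 100 × 3/50 = 6.0 points

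Illustration, with an assumed 25 of 50 subjects at worst grade 3 or higher: the Grade 3-or-higher incidence is 25/50 = 50.0% whatever f is. The Grade 3 and 4 incidence at highest grade is 24/50 = 48.0%, 23/50 = 46.0% or 22/50 = 44.0% for f = 1, 2 or 3.

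**Step 4: how likely the case is to arise.** With an assumed fatal-AE risk p per subject, P(at least one in 50) = 1 − (1 − p)^50:

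| Assumed p | P(at least one fatal AE) |
|---|---|
| 1% | 39.5% |
| 2% | 63.6% |
| 5% | 92.3% |

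These are chances of any fatal AE. Whether each one lowers the overall figure depends on the counting rule in Step 2.

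**The case against.** The strongest reply is that the loss comes from joining two rules that the protocol does not join. The highest-severity rule belongs to the AE severity summary in Section 10.4; Section 10.1 lists an incidence and confines its own worst-grade sentence to selected events. That stands as far as it goes: for an event with an earlier Grade 3 or 4 record, the outcome is ambiguous. It does not help an event that is fatal at onset, and Section 10.9.1 does not guarantee a separate Grade 3 record for one that progresses to death.

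A reader might infer that fatal toxicity is concealed, or that the safety report as a whole understates toxicity where it is worst. The documents do not support that. Death is an SAE criterion (Section 10.6.1), SAE incidence is a listed endpoint, deaths are tabulated, and the Section 10.4 severity summary would show the event at Grade 5 under its own term and class, where Grades 3, 4 and 5 can be added. A figure labelled Grade 3 and 4 is also accurate as labelled.

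A reader might also infer that this will be the figure quoted against other regimens. The protocol does not say so, and the study has no control arm.

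Two further replies stand in part. The printed Grade 5 definition applies formally to events outside CTCAE, although it is the only scale that the protocol prints. And Section 9 leaves analysis details to a formal SAP due before database lock, where the point can be settled; but the endpoint as listed is a stated rule rather than an open detail.

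**Conclusion.** The point holds in a limited form. As written, the severity endpoint excludes Grade 5. Under the Section 10.4 rule an AE that becomes fatal is not in the Grade 3 and 4 incidence for its term and system organ class, and an AE fatal at onset is outside it however events are counted. Fatal events remain visible elsewhere, so the defect lies in one summary measure and not in the disclosure of toxicity.

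The size is up to 2 percentage points per such subject. That assumes 50 treated subjects and, for the overall figure, either highest-grade counting overall or a subject with no other Grade 3 or 4 record. The number of fatal AEs is assumed, so 2 to 6 points for one to three cases is a range and not a forecast. Because safety is descriptive, no test, alpha or power is affected. This is a free improvement, not an error that threatens a conclusion.

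**What to change.** In Section 10.1, replace the endpoint with: incidence of Grade 3 or higher (3, 4 or 5) AEs, by worst grade per subject, overall and by system organ class and preferred term. Show Grade 5 in its own column so that the Grade 3 and 4 counts can still be read.

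Add one condition. Section 10.9.3 puts progression-only deaths on the Adverse Event page, so a plain Grade 3-or-higher count could take them in as Grade 5 AEs. State that deaths attributed solely to disease progression are reported separately and are not counted as Grade 5 AEs.

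The cost is a short wording change in the protocol or SAP and matching table shells, using data already collected. It should be made before database lock, so that results cannot influence the choice.

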10.2 ADVERSE EVENT CHARACTERISTICS

CTCAE term (AE description) and grade: The descriptions and grading scales found in the revised NCI Common Terminology Criteria for Adverse Events (CTCAE) version 4.0 will be utilized for AE reporting. All appropriate treatment areas should have access to a copy of the CTCAE version 4.0. A copy of the CTCAE version 4.0 can be downloaded from the CTEP web site http://ctep.cancer.gov/protocolDevelopment/electronic_applications/ctc.htm.

Expectedness: AEs can be 'Unexpected' or 'Expected' for expedited reporting purposes only. Expected AEs are defined as those described in the ublituximab and TGR-1202 Investigator Brochures.

10.3 DEFINITIONS OF ADVERSE EVENTS

An adverse event (AE) is any untoward medical occurrence in a subject or clinical investigation subject administered a pharmaceutical product. An AE does not necessarily have to have a causal relationship with this treatment. An adverse event (AE) can therefore be any unfavorable and unintended sign (including an abnormal laboratory finding, for example), symptom, or disease temporarily associated with the use of a medicinal product, whether or not considered related to the medicinal product. This includes any occurrence that is new in onset or aggravated in severity or frequency from the baseline condition.

In clinical studies, an AE can include an undesirable medical condition occurring at any time, including run-in or washout periods, even if no study treatment has been administered. The NCI Common Terminology Criteria for Adverse Events (CTCAE) v4.0 is to be used for the grading of

severity of symptoms and abnormal findings. For adverse events not covered by the NCI-CTCAE Version 4.0 grading system, the following definitions will be used:

- **Grade 1:** Mild; asymptomatic or mild symptoms; clinical or diagnostic observations only; intervention not indicated.
- **Grade 2:** Moderate; minimal, local or non-invasive intervention indicated.
- **Grade 3:** Severe or medically significant but not immediately life-threatening; hospitalization or prolongation of hospitalization indicated.
- **Grade 4:** Life-threatening consequences; urgent intervention indicated.
- **Grade 5:** Death related to AE.

10.4 ADVERSE EVENTS (AE'S) AND TREATMENT EMERGENT ADVERSE EVENTS (TEAE'S)

All AEs and SAEs occurring on study will be listed by subject. The frequency and percentages of subjects with treatment-emergent adverse events (TEAEs) will be tabulated by system organ class (SOC) and preferred term (PT), where treatment-emergent is defined as any AE that:

- Occurs after first dosing of study medication and through the end of the study or up through 30 days after the last dose of study treatment, or
- Is considered treatment-related regardless of the start date of the event, or
- Is present before first dosing of study medication but worsens in intensity or the investigator subsequently considers treatment-related.

TEAEs that are considered at least possibly related to study treatment will be tabulated as well as deaths, SAEs, and events resulting in treatment discontinuation.

AEs that occur after informed consent but before first dosing of study medication will not be summarized but will be listed.

At each level of summarization, a subject will be counted only once for each AE, SOC, or PT experienced within that level. In the summation for AE severity, within each level of AE, SOC, or PT experienced, the one with the highest severity will be included. In the summation for AE's relationship to the study drug, within each level of AE, SOC, or PT experienced, the one with the closest relationship to the study drug will be included.

10.5 ADVERSE EVENTS / SERIOUS ADVERSE EVENT CAUSALITY ASSESSMENT

The Investigator must also assess the relationship of any adverse event to the use of study drugs (whether none, one, or both), based on available information, using the following guidelines:

- **Not Related:** Clear-cut temporal and/or mechanistic relation to a cause other than the study drug(s).
- **Doubtful:** There is no reasonable possibility that the event is related to the study drug(s) but a definite cause cannot be ascertained.

- **Possible:** There is still a reasonable possibility that the cause of the event was the study drug(s) but there exists a more likely cause of the event such as complications of progressive disease.
- **Probable:** The most likely cause of the event is the study drug(s) but other causes cannot be completely excluded.
- **Definite:** Clear cut temporal and/or mechanistic relation to the study drug(s). All other causes have been eliminated. Events classified as definite will often be confirmed by documenting resolution on discontinuation of the study drug and recurrence upon resumption.

10.5.1 RECORDING OF ADVERSE EVENTS

All adverse events of any subject during the course of the study will be reported on the case report form, and the investigator will give his or her opinion as to the relationship of the adverse event to study drug treatment (i.e., whether the event is related or unrelated to study drugs administration – umbralisib and/or ublituximab). If the adverse event is serious, it should be reported as soon as possible and no greater than 24 hours to the sponsor or designee. Other untoward events occurring in the framework of a clinical study are also to be recorded as AEs (i.e., AEs that occur prior to assignment of study treatment that are related to a protocol-mandated intervention, including invasive procedures such as biopsies, medication washout, or no treatment run-in).

All AEs regardless of seriousness or relationship to umbralisib and/or ublituximab treatment spanning from Cycle 1/Day 1 until 30 calendar days after discontinuation or completion of either protocol-specific treatment as defined by the protocol for that subject, are to be recorded on the eCRF.

10.5.2 ABNORMAL LABORATORY VALUES AND VITAL SIGNS

The reporting of abnormalities of vital signs as adverse events should be avoided. Abnormalities of vital signs should not be reported unless any criterion for an SAE is fulfilled, the vital signs abnormalities cause the subject to discontinue study treatment, or the investigator insists that the abnormality should be reported as an AE. Abnormal laboratory results should be noted in the eCRF as an adverse event if they are associated with an overdose, require or prolong inpatient hospitalization, or are otherwise considered clinically significant by the investigator. If an abnormal laboratory value or vital sign is associated with clinical signs and/or symptoms, the sign or symptom should be reported as an AE, and the associated laboratory value or vital sign should be considered additional information that must be collected in the relevant eCRF. If the lab abnormality is a sign of a disease or syndrome, only the diagnosis needs to be recorded on the SAE Form or AE eCRF.

Clinical Laboratory Results will be summarized. Summary statistics for actual values and for changes from baseline will be tabulated for laboratory results by scheduled visit. Subjects with laboratory values outside of the normal reference range at any post-baseline assessment will be summarized, and graded per NCI CTCAE Version 4.0 when applicable. Subject incidence of abnormal lab results will be summarized by treatment group and maximum grade for each abnormal lab finding.

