9 STATISTICAL CONSIDERATIONS

The sections of the Statistical Considerations describe the statistical methods to be used to analyze the efficacy and safety. These methods may be revised and updated due to reasons such as regulatory requirements or need for further clarifications. The final analysis plan will be documented in a formal statistical analysis plan (SAP) that must be finalized before database lock. The SAP will include details on how variables will be derived, how missing data will be handled, and how censoring procedures will be applied to time to event related variables as well as the details on statistical methods to be used for safety and efficacy analyses. The final clinical study report will discuss deviations from the SAP, if any.

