10.6 SERIOUS ADVERSE EVENTS

10.6.1 DEFINITIONS OF SERIOUS ADVERSE EVENTS

The definitions of serious adverse events (SAEs) are given below. The investigator is responsible for ensuring that all staff involved in the study are familiar with the content of this section.

An SAE or reaction is defined as any untoward medical occurrence that:

- results in death, is immediately life-threatening,
- requires at least a 24-hour in-patient hospitalization or prolongation of existing hospitalization,
- results in persistent or significant disability/incapacity, and/or
- causes a congenital anomaly/birth defect.

Medical and scientific judgment should be exercised in deciding whether expedited reporting is appropriate in other situations, such as important medical events that may not be immediately life-threatening or result in death or hospitalization, but may jeopardize the subject or may require intervention to prevent one of the other outcomes listed in the previous definition. These should also usually be considered serious. Examples of such events are intensive treatment in an emergency room or at home for allergic bronchospasm; blood dyscrasias or convulsions that do not result in hospitalization; or development of drug dependency or drug abuse.

Progression of malignancy (including fatal outcomes), if documented by use of appropriate method (for example, as per Cheson et al. 2007, should not be reported as a serious adverse event.

A suspected unexpected serious adverse reaction (SUSAR) is defined as an SAE that is suspected to be at least possibly related to study medication(s) and is an unexpected event. SUSAR reporting is encompassed within SAE reporting guidelines as defined in this section.

Treatment within or admission to the following facilities is not considered to meet the criteria of "in-patient hospitalization" (although if any other SAE criteria are met, the event must still be treated as an SAE and immediately reported):

- Emergency Department or Emergency Room
- Outpatient or same-day surgery units

- Observation or short-stay unit
- Rehabilitation facility
- Hospice or skilled nursing facility
- Nursing homes, Custodial care or Respite care facility
- Admission for study related treatment

Hospitalization during the study for a pre-planned surgical or medical procedure (one which was planned prior to entry in the study), does not require reporting as a serious adverse event to the Sponsor.

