10.9 DIAGNOSIS VS. SIGNS AND SYMPTOMS

All AEs should be recorded individually in the subject's own words (verbatim) unless, in the opinion of the Principal Investigator or designated physician, the AEs constitute components of a recognized condition, disease, or syndrome. In the latter case, the condition, disease, or syndrome should be named rather than each individual sign or symptom. If a constellation of signs and/or symptoms cannot be medically characterized as a single diagnosis or syndrome at the time of reporting, each individual event should be recorded as an AE or SAE as appropriate on the relevant form(s) (SAE Report Form and/or AE eCRF). If a diagnosis is subsequently established, it should be reported as follow-up information is available. If a diagnosis is determined subsequent to the reporting of the constellation of symptoms, the signs/symptoms should be updated to reflect the diagnosis.

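### Section 10.5.2 makes not recording vital-sign abnormalities as AEs the default, the reverse of its laboratory rule, so some symptom-free changes may be missing from AE tables (minor)

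*Combined protocol and SAP*

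**What the plan says.** Section 10.5.2 gives two recording rules in one paragraph.

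- **Vital signs.** The opening instruction is "The reporting of abnormalities of vital signs as adverse events should be avoided". Three exceptions follow: any SAE criterion is met, the abnormality causes the subject to stop study treatment, or "the investigator insists that the abnormality should be reported as an AE".
- **Laboratory results.** These are to be entered as AEs if they are linked to an overdose, require or prolong hospitalization, or "are otherwise considered clinically significant by the investigator". Section 10.9.2 repeats this rule for laboratory values.

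The same paragraph says that when either kind of abnormality comes with signs or symptoms, the sign or symptom is the AE and the measurement is supporting information.

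Section 10.3 defines an AE broadly enough to include an unfavorable, unintended sign, whether or not the drug caused it. Section 10.5.1 asks for all AEs to be reported, regardless of seriousness or relationship, from Cycle 1 Day 1 to 30 days after treatment ends. Pulse, blood pressure, temperature, weight and respiration are measured at scheduled visits (Section 5).

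**The concern.** The two rules start from opposite positions. For a laboratory value, the investigator's view that it matters is enough. For a vital sign, the instruction is not to report, and the investigator has to override it. A site that follows the text as written could leave out a change that is an AE under 10.3.

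Evaluating safety is a secondary objective, and incidence of AEs is one of the safety endpoints in 10.1. Section 7.2.1.2 lists weight decreased and hypertension among events at least possibly related to the combination, both in the band from 1% to under 10%. Both can first show up as a measurement rather than a complaint. If such a change is not entered, it has no causality assessment under 10.5 and does not reach the treatment-emergent AE tables under 10.4.

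**Working it through.** No sample size, power or error rate is involved, so the check is a comparison of texts.

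**Step 1. Compare the two triggers in 10.5.2.**

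| Situation | Vital sign | Laboratory value |
|---|---|---|
| Default | Avoid reporting | Record when a trigger is met |
| Investigator thinks it clinically significant | Not a trigger; the investigator must insist | Trigger |
| SAE criterion | Named (any) | Hospitalization named |
| Stops study treatment | Named | Not named separately |
| Overdose | Not named | Named |
| Leads only to new treatment, a dose hold or a dose reduction | Not named | Not named, but open to the clinical-significance judgment |

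The lists are not nested: each names something the other does not. The vital-sign rule is stricter in its default and in what it asks of the investigator, not on every line.

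**Step 2. Compare with the general AE rules.** An unfavorable sign is an AE under 10.3, and 10.5.1 asks for all AEs. The laboratory rule also narrows 10.3, but by a clinical filter. The vital-sign rule narrows it by discouraging the entry itself. That is the conflict.

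**Step 3. Trace which cases survive.**

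- Symptomatic: captured through the symptom (10.5.2).
- Diagnosed: captured, because under 10.9 "the condition, disease, or syndrome should be named rather than each individual sign or symptom".
- Worsened pre-existing condition: captured under 10.9.5.
- Serious: captured. Section 10.6.1 extends this to important medical events, saying "These should also usually be considered serious".
- Leading to discontinuation, or insisted on by the investigator: captured by the exceptions.
- Non-serious, symptom-free, undiagnosed and not leading to discontinuation: falls to the default. This includes a change that led only to treatment, a dose hold or a dose reduction.

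**Step 4. Follow the last group into the tables.** Under 10.1, "Worst toxicity grades per subject will be tabulated for select adverse events and laboratory measurements by using NCI CTCAE criteria v4.0". Under 10.5.2, "Summary statistics for actual values and for changes from baseline will be tabulated for laboratory results by scheduled visit". Neither sentence names vital signs. Section 9.2 does say that listings will contain all available safety data, so the measured values should be visible there. A listing shows the value. It does not supply the site's AE entry, its grade or its causality assessment.

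**Step 5. Can the loss be sized?** No. That would need the share of weight or blood-pressure changes that are symptom-free and undiagnosed, and the share of those that sites would leave out. The documents give neither.

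**The case against.** The strongest reply is that nothing is barred. The investigator's override has no threshold, so anything an investigator thinks worth recording can be recorded, and insisting differs from finding clinical significance mainly in tone. This largely stands and is why the point is minor. What remains is the default: some sites will follow an instruction to avoid an entry without weighing each case.

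Four stronger readings are tempting, and the documents do not support them.

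- *Vital-sign AEs are lost in general.* A reader might infer this from the opening sentence. Step 3 shows that most important cases have another route in.
- *The under-count can be estimated from the listed rate for weight decreased.* That rate covers all such events at least possibly related to treatment, with or without symptoms. Section 7.2.1 does not say which reporting rule its source used. Any missed share would be pure assumption. An exact interval around an AE proportion would not help either, since 10.1 plans no inferential analysis of safety.
- *Blood-pressure changes around ublituximab infusions will go unrecorded.* Section 6.2.2 does warn of infusion-related hypotension and of withholding antihypertensives. Such changes fall largely within recognised infusion reactions, which 7.2.1.1 lists as very common events and which can be entered under that diagnosis.
- *The lack of a named vital-sign table is itself a defect.* Section 9 leaves this to a later SAP, which is to cover derivations and censoring "as well as the details on statistical methods to be used for safety and efficacy analyses", and 9.2 already provides listings. The absent table is deferred detail.

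**Conclusion.** The point holds in a limited form. Section 10.5.2 states a recording default that conflicts with 10.3 and 10.5.1 and differs from the laboratory rule beside it. Followed as written, it can leave non-serious, symptom-free, undiagnosed changes, such as weight loss or raised blood pressure, out of AE tables. A later SAP can tabulate the measurements but cannot restore AE entries that sites did not make.

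The size is unknown and the consequence is minor: it is confined to descriptive tables for a secondary safety objective, and ORR is unaffected. The conclusion assumes that at least some sites follow the default rather than override it, which the documents can neither confirm nor exclude. It is worth acting on because the correction is cheap.

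**What to change.** In 10.5.2, replace the wording that discourages vital-sign reporting, and the list of exceptions after it, with the laboratory trigger. For example: *Record a vital-sign abnormality as an AE if the investigator considers it clinically significant, if it leads to treatment, a dose hold, a dose reduction or discontinuation of study drug, or if it meets an SAE criterion.* Keep the existing rule that an associated symptom or diagnosis is recorded instead of the measurement, so that one event is not entered twice.

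The cost is a small protocol wording change and some additional AE entries for sites. No new assessments are needed, because the vital signs are already in the schedule.
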